2.2.2 Nivolumab in RCC

Motzer et al. published results of a phase 2 trial of the PD1 inhibitor nivolumab in metastatic RCC, demonstrating an objective response rate of 20%, 22%, and 20% and median OS of 18.2, 25.5, and 24.7 months for doses of 0.3, 2, and 10 mg/kg given intravenously every 3 weeks, respectively. Responses occurred more commonly in PD-L1 expressing tumors ($\geq 5\%$ PD-L1 expression) with overall response rate (ORR) of 31%, but the ORR of 18% for tumors expressing $< 5\%$ PD-L1 is still among the best ORRs in RCC. Median OS was not reached in the PD-L1 $\geq 5\%$ group and was 18.2 months in the PD-L1 $< 5\%$ group, the latter similar to that achieved with axitinib therapy in the second-line setting.³⁷ Some responding patients continued to respond for nearly a year after cessation of therapy.³⁸ Subsequently, results of the CheckMate 025 trial, where patients with advanced RCC previously treated with 1 or 2 regimens of antiangiogenic therapy were randomized to receive either nivolumab 3 mg/kg given q 2 weekly vs. everolimus 10 mg by mouth daily, were reported, demonstrating a median OS of 25 months with nivolumab and 19 months with everolimus. The ORR with nivolumab was 25% (vs. 5% with everolimus). Grade 3 and 4 events were less common with nivolumab (19%) than with everolimus (37%).³⁹

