2.2.3 Anti-angiogenic plus PD1 Inhibitor Combination Trials

Studies combining anti-angiogenic therapies and PD1 inhibitors in RCC have recently been performed. A trial of nivolumab plus sunitinib confirmed that combining each agent at full dose was tolerable (nivolumab up to 5 mg/kg IV q 3 weekly; sunitinib 50 mg PO daily 4 weeks on/2 weeks off) and demonstrated objective anti-tumor activity (41% ORR by 6 weeks); however, hepatotoxicity was noted. Similarly, combining nivolumab with pazopanib resulted in increased toxicity, notably hepatotoxicity. Specifically, in trial NCT01472081, patients with mRCC (≥ 1 prior systemic therapy) received nivolumab in combination with sunitinib (50 mg, 4 weeks on/2 weeks off; Arm S) or pazopanib (800 mg daily; Arm P), until progression/unacceptable toxicity. The starting dose of nivolumab was 2 mg/kg IV Q3W (N2), with planned escalation to 5 mg/kg IV Q3W (N5). Based on tolerability, the Arm S N5 cohort was expanded to treatment-naïve patients. Primary objectives were safety/tolerability and determination of maximum tolerated dose (MTD) for the combinations; the secondary objective was antitumor activity (ORR and duration of response [DOR]). Seven patients were assigned to each of Arms S N2 and N5. No dose-limiting toxicities (DLTs) were observed and a MTD was not reached, thus N5 was expanded with 19 additional patients (total n=33). Arm P enrolled 20 patients at N2; 4 DLTs (elevated ALT/AST [n=3], fatigue [n=1]) were observed, leading to closure of this arm. Grade 3–4 related AEs were observed in 24/33 patients (73%) in Arm S and 12/20 patients (60%) in Arm P. The most common related Grade 3–4 AEs included elevated ALT (18%), hypertension and hyponatremia (15% each) in Arm S and elevated ALT/AST (20% each) and fatigue (15%) in Arm P. Hepatotoxicities were manageable using treatment algorithms. Grade 3 pneumonitis occurred in 1 patient (Arm S, N5). Grade 3–4 related AEs led to therapy discontinuation in 8/33 patients

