Each cycle of therapy will be 4 weeks. Tumor disease evaluation will occur after Cycles 2, 4, 6, 9, 12, and then every 4 cycles thereafter, or at any time clinical progression is suspected. If pseudoprogression is suspected (until any degree of response is observed), disease evaluation must occur after every cycle ([Section 10.2.1](#)). Absent disease

progression or unacceptable toxicity, patients may continue on protocol therapy for up to 2 years duration or completion of 26 cycles, whichever comes first. Disease evaluations (including imaging) will continue during follow-up according to the schedule outlined in [Section 7.2](#).

For patients who progress on Arm C prior to Cycle 22, cross-over to Arm A is permitted. Patients should resume Arm A therapy as soon as PD is identified. Nivolumab should continue uninterrupted according to the previously established schedule for that patient (either every 2 or 4 weeks). Axitinib should be added as soon as it becomes available from NCI and the patient has recovered from any relevant toxicity. Subsequent disease evaluations should occur as above timed from the first cycle of combination therapy. The first cycle of combination therapy after cross-over will be defined as the cycle for which > 14 days of axitinib is given, with Day 1 of Cycle 1 after cross-over defined as the day of first nivolumab dose during that cycle after axitinib is started or on the day axitinib is started if given concurrently. **NOTE:** The total protocol therapy received on AREN1721 (whether delivered on Arm A, Arm C, or Arm C+A) is not to exceed 26 cycles or 2 years, whichever comes first.

NOTE:

- Patients who have not had cytoreductive nephrectomy prior to trial enrollment but who elect to have cytoreductive nephrectomy during therapy may remain on protocol therapy.
- Cytoreductive therapy is not permitted in the first 12 weeks after starting protocol therapy.
- Axitinib must be held for 7 days before and after surgery. See [Section 13.1.2](#) for more details.

For COG Supportive Care Guidelines see:

<https://childrensoncologygroup.org/index.php/cog-supportive-care-guidelines>.

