***Axitinib dose titration:**

Individual patient dose titration of axitinib (escalation from starting dose) is permitted on protocol therapy, at the discretion of the treating physician, if the following criteria are met for an individual patient:

1. Two consecutive cycles are completed at a given dose without any adverse reactions $>$ Grade 2 (according to the Common Toxicity Criteria for Adverse Events [CTCAE]).
2. The patient is normotensive, and not receiving anti-hypertension medication.

For patients \geq 18 years old, when a dose increase from 5 mg twice daily is recommended, the axitinib dose may be increased by 1 mg/dose twice daily (for example, from 5 mg twice daily to 6 mg twice daily, etc), up to a maximum of 10 mg twice daily. No more than 1 dose titration can occur in each 2-cycle period per the criteria above. Refer to the table in [Section 5.2.1.1](#) for additional detail.

For patients < 18 years old, see [Appendix IV](#) for dose titration nomograms. No more than 1 dose titration can occur in each 2-cycle period per the criteria above. The maximum titration dose is as per the Dose Level 3 table in [Appendix IV](#).

Nivolumab: IV over 30 minutes, or per institutional guidelines

Age	Dose and Days
≥ 18 years old	Either 240 mg/dose on Days 1 and 15 OR 480 mg/dose on Day 1 only
< 18 years old	3 mg/kg/dose (maximum 240 mg/dose) on Days 1 and 15

The risk of infusion reactions with nivolumab is low and no pre-medications are required. Monitoring for infusion reactions should be per institutional guidelines. Please refer to [Section 5.3.2](#) for suggested infusion reaction management guidelines.

Nivolumab will be distributed by the Division of Cancer Treatment and Diagnosis (DCTD), NCI. Do not use commercial supply.

See [Section 5.0 for Dose Modifications based on Toxicities.](#)

Following completion of a cycle, begin next cycle on Day 29 or when criteria to begin cycle are met, whichever occurs later.

4.4 Arm B: Axitinib (For patients enrolled and randomized to Arm B prior to Amendment 2A) Closed to new accrual with Amendment 2A

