9.0 STATISTICAL CONSIDERATIONS

9.1 Sample Size and Study Duration

As of Amendment 5A, which now allows crossover upon progression from the nivolumab arm to the nivolumab + axitinib arm, we expect enrollment of approximately 2 patients per month. This is derived from tRCC prevalence, access to treatment centers, and enrollment patterns to date, which should be aided by the crossover.

To reduce the overall sample size from the prior design, we have maintained the same overall study design but changed two design parameters: 1-sided alpha will be increased from 0.05 to 0.15, and the targeted hazard ratio will be reduced from $HR = 0.50$ to $HR = 0.40$. With these changes, 22 PFS events will be required to address the primary objective comparing Arms A and C at the time of final analysis (see [Section 9.2](#)). Allowing that approximately 25% of eligible and evaluable patients may not have experienced a PFS event by the time of the final analysis, the target accrual on this study is 28 patients. To account for an additional estimated 5% of patients who might be found to be ineligible for the study or inevaluable for the primary endpoint at the time of or following study enrollment (e.g., due to randomization to Arm B, no central path review performed, or having central path review confirming a diagnosis other than tRCC), the ceiling accrual will be set to 40 patients, including those patients already enrolled.

If the study accrues to the target accrual without interim stopping for futility, the additional time required to enroll up to this maximum once re-opening under Amendment 5A is estimated to be 14 months. As before, all eligible patients will be followed for 5 years after randomization, and the final analysis will be conducted once the target number of PFS events needed for the final analysis has been reached, or after 2 years of follow-up is obtained for the last patient enrolled, whichever occurs first.

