9.4 Endpoints and Evaluability

The primary endpoint is progression-free survival (PFS), which is defined as the time from randomization to the earliest occurrence of disease progression (as defined by modified RECIST criteria for immunotherapy, described in [Section 10](#)) or death due to any cause among patients who initiated protocol treatment. Patients not experiencing a PFS event by the time of a prospectively-planned interim or final analysis will be right-censored at the time of their most recent response/progression evaluation. Following the intent-to-treat principle, all patients who are randomized and confirmed to have tRCC by central pathology review will be evaluable for PFS. Patients randomized to Arm B prior to Amendment 2A, and patients who have a central path review confirming a diagnosis other than tRCC, or who never receive central path review per protocol, will be considered inevaluable for the primary endpoint comparison but included in study descriptive statistics.

The overall response rate (ORR) will be defined as the rate of complete or partial responses (assessed by imaging) among patients who initiated protocol therapy and completed at least one subsequent imaging assessment. Patients who are randomized to Arms A or C and are confirmed to have tRCC by central pathology review will be evaluable for ORR.

Overall survival (OS) will be calculated as the time from randomization to death due to any cause, with surviving patients being right-censored at their length of follow-up at the time of analysis. Patients who are randomized to Arms A or C and are confirmed to have tRCC by central pathology review will be evaluable for OS.

Note: For calculations of both PFS and ORR, any lesions resected during protocol therapy for reasons other than progression (as noted by sites or documented upon central surgical review) will not contribute toward response/progression assessments. Response/progression assessments are scheduled to take place after Cycles 2, 4, 6, 9, 12, and then every 4 cycles thereafter, after every cycle following any suspected pseudoprogression until the total tumor burden subsequently diminishes, or at any time clinical progression is suspected. Once in follow-up, patients without a documented PFS event will be evaluated according to the schedule in [Section 7.2](#). ORR and OS will be analyzed as a part of exploratory aim 1.3.1.

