Patients in whom the magnitude of increase in tumor size is $\geq 20\%$ but $< 40\%$ from baseline may remain on protocol therapy **for up to 12 weeks after start of protocol therapy** if all of the following criteria are met, to allow for the possibility of pseudoprogression followed by a later tumor response (which may occur during treatment with immunotherapy):

- In the judgment of the treating clinician, the patient does not show evidence for rapid disease progression or the patient has shown evidence for clinical benefit.
- There is no decrease in performance status.
- The patient is tolerating the study drug and there has been no DLT (see [Section 5.1](#)).
- Continued treatment with nivolumab alone or in combination with axitinib will not delay an imminent intervention required to prevent a serious complications (e.g. CNS metastases which require radiation therapy or surgery).

For response assessments occurring during the first 12 weeks on protocol therapy, new lesions with a longest diameter of $< 10\text{ mm}$ (or newly noted lymph nodes with short axis $< 15\text{ mm}$) should not be counted toward the total tumor burden. Only new lesions with a longest diameter $\geq 10\text{ mm}$ (or lymph nodes with short axis $\geq 15\text{ mm}$) should be included in the total tumor burden and assessments of percentage change from baseline or nadir.

For patients who remain on protocol therapy despite an increase in tumor burden $\geq 20\%$ (possible pseudoprogression) during the first 12 weeks, imaging to include target lesions must occur every cycle, and the same radiographic and clinical criteria must be met in order to remain on protocol therapy. If tumor burden subsequently diminishes to $< 20\%$ increase from baseline or nadir, the patient may

be followed according to the standard protocol guidelines which will involve less frequent imaging. The decision to continue treatment beyond radiographic evidence for disease progression ($\geq 20\%$ increase in tumor burden) may be discussed with the study PI and should be documented in the study record.

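### On-treatment imaging is counted in cycles while PFS runs in calendar time, so any excess of cycle-start delays in Arm A would bias PFS towards Arm A

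*Combined protocol and SAP*

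**What the plan says.** Section 4.1 sets the schedule: "Tumor disease evaluation will occur after Cycles 2, 4, 6, 9, 12, and then every 4 cycles thereafter". The same sentence adds a scan whenever clinical progression is suspected. Section 9.4 repeats the count for the primary endpoint: "Response/progression assessments are scheduled to take place after Cycles 2, 4, 6, 9, 12". Sections 4.3.2, 4.5.2, 10.2 and 16.2 also count in cycles.

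Cycles need not last 28 days. Section 4.3.3 tells sites to "begin next cycle on Day 29 or when criteria to begin cycle are met, whichever occurs later", and Section 4.5.3 has the same rule for Arm C. The neutrophil and platelet criteria for starting a cycle are the same in both arms, and both refer on to Section 5.0 for ongoing toxicity.

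PFS runs from randomization (Sections 9.2 and 9.4). The 72-hour allowance in Section 4.0 limits departures from a schedule that is itself counted in cycles, so it does not cap a shift caused by a late cycle. Section 9 contains no calendar anchor, nominal-visit analysis or interval-censored analysis.

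On suspected pseudoprogression, Section 4.1 requires that, "until any degree of response is observed), disease evaluation must occur after every cycle". Section 10.2.1 instead lets a patient whose burden has fallen back below a 20% increase "be followed according to the standard protocol guidelines which will involve less frequent imaging". Section 9.4 ends every-cycle imaging when burden diminishes, and Section 10.2 when a later response is documented.

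**The concern.** A progression found on a scheduled scan takes the date of that scan. If scans in one arm drift later for reasons unrelated to the tumour, that arm's PFS lengthens without any treatment effect. The log-rank test uses only the order of events. A shift of a week can therefore place an Arm A event behind every Arm C event found at the same nominal visit.

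The drift could plausibly be larger in Arm A. It gives both agents at full single-agent dose (Section 4.1), and Section 5.2 adds axitinib holds of up to 21 days that have no counterpart in Arm C.

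The trial has little room for a systematic error. It has 22 events, and Section 9.1 already states that "1-sided alpha will be increased from 0.05 to 0.15". The futility rule (stop if the observed hazard ratio exceeds 1.00 at 11 events) rests on the same dates.

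**Working it through.** **Inputs from the protocol (Sections 9.1 to 9.3).** One-sided alpha 0.15; target HR 0.40; 22 events; 28 patients randomized 1:1; futility stop at 11 events if HR > 1.00; accrual 24 per year; follow-up capped at 2 years after the last patient.

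**Assumptions.** Exponential PFS with control medians between 3 and 8.2 months (the planned piecewise model is in a figure that is not shown); unstratified log-rank test; delay rates chosen for illustration, since none is given.

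**Step 1: reproduce the plan.** With z(0.85) = 1.0364 and z(0.80) = 0.8416, the squared sum is 3.527.
- Schoenfeld events: 4 × 3.527 / (ln 0.4)² = 16.8, so 17.
- Freedman events: (1.4/0.6)² × 3.527 = 19.2, so 20. The planned 22 leaves room for the futility look.
- Futility stop at HR 0.4: Φ(−√11 × 0.6/1.4) = Φ(−1.42) = 7.8% (plan: 8%).
- Efficacy with both looks (bivariate normal): 81.0% at HR 0.4, 67.2% at HR 0.5 and 13.9% at HR 1.0 (plan: 80%, 66%, 14%).
- Simulation on the protocol's scan grid without delay: power 80.5-81.9%, type I error 14.0-14.5%.

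**Step 2: convert cycles to weeks.** At 4 weeks per cycle, Cycles 2, 4, 6, 9 and 12 end at weeks 8, 16, 24, 36 and 48, and every 4 cycles is every 16 weeks. If Cycle 2 starts 2 weeks late, those five scans fall at weeks 10, 18, 26, 38 and 50.

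**Step 3: shift the scans under a true HR of 1.0.** The entries are the chance of declaring efficacy.

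| Delay pattern | Progression found only on scheduled scans | Half of events dated off schedule |
|---|---|---|
| Scans fixed to calendar weeks | 14.3-14.5% | not run |
| Same delays in both arms | 14.1-14.3% | not run |
| 5-20% of Arm A cycles, 1-3 weeks; none in Arm C | roughly 15-20% | about 14-17% |
| One-off 1- or 3-week delay in 20-50% of Arm A patients | 15.9-20.3% | 14.7-16.0% |
| One-off 6-week delay in 30% of Arm A patients | 14.8-15.0% | 14.2-14.7% |
| 2-week delay in 25% of Arm A and 10% of Arm C cycles | 16.9% | not run |
| 1-3 week delays in 10-50% of Arm A cycles | 15.1-27.5% | 14.4-18.4% |

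Monte Carlo error is about 0.2-0.5 points. The third row depends on how visit timing is coded. Scans falling exactly on the grid gave 14.5-15.8%. Spreading visits by ±3 days gave 15.1-17.7% in one run, and other runs of the same delay model gave 16-19% and 17-20%. The effect does not grow steadily with delay length, because a longer gap also collects more progressions per scan.

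**Step 4: other operating characteristics.** With one-off 1- or 3-week delays in Arm A and scheduled scans only, futility stopping at HR 1.0 falls from 50% to 42.5-47.2%. Apparent power at HR 0.4 rises to 82.6-85.9%.

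**The case against.** The strongest reply is that nothing in the documents shows Arm A cycle starts slipping more than Arm C's. The start criteria, the Day 29 rule and the 6-week nivolumab limit (Section 5.3.5) are common to both arms. Section 5.2.2 allows axitinib breaks of up to 7 days within a cycle, and no text says that an axitinib hold stops the cycle count. After cross-over, nivolumab continues uninterrupted and a cycle counts with just over 14 days of axitinib, which suggests that the count can run on. This stands: the excess is an inference.

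A reader might infer from Section 2.2 that Arm A will certainly be delayed more: "related AEs were observed in 24/33 patients (73%) in Arm S", against 19% Grade 3-4 events for nivolumab alone in Section 2.2.2. The documents do not support that step. The 73% is for sunitinib plus nivolumab, the 19% comes from a different trial, and both are patient-level event rates rather than cycle delays. Section 2.2.3 also reports axitinib with another PD1 inhibitor as tolerable at full doses.

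Unscheduled scans and deaths are dated off schedule and dilute the effect. That also stands, and it is why the right-hand column of the table is lower.

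What the reply does not remove is the link itself. Scans move with cycles, PFS does not, and the plan has no safeguard if delays turn out to be unequal.

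**Conclusion.** The concern holds as a conditional bias. If cycle starts are delayed more in Arm A, recorded progression moves later and PFS favours Arm A; no simulated scenario reversed that direction. For delays in 5-20% of Arm A cycles and none in Arm C, type I error goes from about 14% to roughly 15-20% with scheduled detection only, and to about 14-17% if about half of events are dated off schedule. Equal delays give no bias. The highest figures in the table need frequent short delays confined to Arm A and no off-schedule detection, and should not be read as expected.

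These sizes rest on assumed delay rates, exponential PFS and an unstratified test, and they ignore patients already enrolled. The documents do not support saying that the primary comparison is biased, only that it is exposed to a bias that is cheap to remove.

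The differing rules for ending every-cycle imaging after suspected pseudoprogression are a separate inconsistency. They apply to both arms, and no between-arm bias is shown.

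**What to change.** For the randomized treatment period up to first progression, time scans at weeks 8, 16, 24, 36, 48 and then every 16 weeks from randomization in both arms, regardless of dose delays. Keep the scans for suspected progression and the separate imaging reset after cross-over, which concerns only the period after the primary event. Edit Sections 4.1, 4.3.2, 4.5.2, 9.4, 10.2 and 16.2, and state whether an axitinib hold stops the cycle count.

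Add to Section 9.3 a PFS sensitivity analysis using nominal visit dates or interval censoring. It also covers patients already imaged by cycle.

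Separately, reconcile Sections 4.1, 9.4, 10.2 and 10.2.1 so that a single rule says when every-cycle imaging ends.

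The cost is mostly wording. Therapy is projected to start within five days of enrollment (Section 3.1.5), so week counts stay close to cycle counts when treatment runs on time, and no extra scheduled scans are then needed. The downsides are that some scans will not fall on a cycle-start visit and that already enrolled patients will have mixed schedules. In simulation, calendar timing gives 14.3-14.5% type I error and 80.5-81.5% power at HR 0.4, in line with the plan.

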4.2 Concomitant Therapy

- 4.2.1 Patients may not receive other anti-cancer medications while on protocol therapy.
- 4.2.2 Small port radiotherapy and/or surgery for management of persistent and/or symptomatic tumor is permitted while on protocol therapy.
- 4.2.3 Patients may not have surgical resection of the tumor during the first 12 weeks of protocol therapy per [Section 13.1.8.1](#).
- 4.2.4 Patients who have surgical resection of lesions that are increasing in size while on therapy must be removed from protocol therapy per [Section 13.1.8.2](#).
- 4.2.5 If not done prior to study enrollment, cytoreductive nephrectomy should be reconsidered after 12 weeks of protocol therapy, taking into account the need to hold axitinib before and after surgery per [Section 13.1.8.3](#).
- 4.2.6 Supportive care per institutional guidelines is permitted.
- 4.2.7 Steroid therapy is permitted as clinically indicated, though it is recommended that use of steroids in patients on nivolumab be limited to use for management of

immune-related adverse events per standard guidelines (see [Section 5.3](#) for Dose Modifications).

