10.2 Response Criteria for Patients with Solid Tumors

Response and progression will be evaluated in this study using the new international criteria proposed by the revised Response Evaluation Criteria in Solid Tumors (RECIST) guideline (version 1.1), with the exceptions described in [Section 10.2.1](#) below to account for possible "pseudoprogression" during treatment with immunotherapy (iRECIST).⁶² The major change in iRECIST is the concept of allowing for the possibility of "pseudoprogression", which occurs when standard RECIST v1.1 progression (> 20% increase in tumor burden from baseline) during the first 12 weeks of treatment is followed at the next assessment by tumor shrinkage.⁶³ Consistent with iRECIST and this definition of pseudoprogression, in the current study, further progression above and beyond the usual 20% threshold will be required to meet the definition of progressive disease for any patient who has not yet completed 12 weeks of protocol therapy.

Following baseline evaluation and treatment initiation, patients should be re-evaluated for lesion response or progression after Cycles 2, 4, 6, 9, 12 and then every 4 cycles thereafter with additional imaging required (1) after every cycle following possible pseudoprogression until subsequent response is documented, and (2) at any time clinical progression is expected. During follow-up, repeat imaging evaluations should occur according to the schedule described in [Section 7.2](#). Confirmatory scans should also be obtained 6-8 weeks (not less than 4 weeks) following initial documentation of objective response.

At each imaging timepoint, the largest diameter (unidimensional measurement) of each target, non-target, or new lesion and the shortest diameter (axis) for each malignant lymph node should be recorded. Any lesions that were surgically resected since the last imaging assessment should be explicitly noted, along with the date and rationale for removal, and an indication of whether the lesion had been increasing in size at the time of surgical removal.

IMPORTANT NOTE: *All calculations of percentage change in total tumor burden to assess response or progression should fully exclude from consideration any malignant lesions that were surgically resected at any time prior to the most recent response assessment.*

10.2.1 Exceptions for Possible Delayed Response ('Pseudoprogression') – only applicable for patients on Arms A and C

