10.2.5 Response Criteria

10.2.5.1 Evaluation of Target Lesions

IMPORTANT: *All calculations of percentage change in total tumor burden to assess response or progression should fully exclude from consideration any malignant lesions that were surgically resected at any time prior to the latest response assessment.*

Complete Response (CR): Disappearance of all target lesions. Any pathological lymph nodes (whether target or non-target) must have reduction in short axis to < 10 mm.

Partial Response (PR): At least a 30% decrease in the sum of the diameters of target lesions, taking as reference the baseline sum diameters.

Progressive Disease (PD): At least a 20% increase in the sum of the diameters of target lesions, taking as reference the smallest sum on study (this includes the baseline sum if that is the smallest on study). In addition to the relative increase of 20%, the sum must also demonstrate an absolute increase of at least 5 mm. See [Section 10.2.1](#) for exceptions during the first 12 weeks.

At least a 40% increase in the sum of diameters of target lesions at any time during the study, taking as reference the smallest sum measured on study (this includes the baseline sum if that is the smallest on study).

Appearance of one or more new lesions is also considered progression. See [Section 10.2.1](#) for exceptions during the first 12 weeks.

For patients who achieve a CR, either due to protocol therapy or surgical resection of any remaining malignant lesions, occurrence of a new lesion ≥ 10 mm or the short axis of a lymph node increasing to ≥ 15 mm at any time is considered PD.

An initial response (any decrease in tumor size) followed by growth of at least 20% (relative to the nadir) at any time is considered PD.

Patients who are removed from protocol therapy for resection of lesions that are increasing in size (per [Section 13.1.8.2](#)) will be considered to have PD at the time of tumor resection.

Stable Disease (SD):

Neither sufficient shrinkage to qualify for PR nor sufficient increase to qualify for PD, taking as reference the smallest sum diameters while on study.

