13.1.8.2 Restrictions for Patients with Tumor Growth

Any surgical tumor resection performed for lesions that are increasing in size (any increase in size based on radiology) will result in removal from protocol therapy.

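### A target lesion irradiated on study stays in the tumour sum by default, so its shrinkage can score a response and, between two scans, can delay a progression call

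*Combined protocol and SAP*

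**What the plan says.** Section 4.2.2 allows local treatment during protocol therapy: "Small port radiotherapy and/or surgery for management of persistent and/or symptomatic tumor is permitted while on protocol therapy". The wording is not limited to lesions outside the target set.

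For surgery, the endpoint consequences are spelled out:

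- Section 10.2 says that percentage-change calculations "should fully exclude from consideration any malignant lesions that were surgically resected at any time prior to the most recent response assessment". The note to 8.1 and section 10.2.5.1 carry the same rule.
- Section 9.4 applies it to both PFS and ORR, for "any lesions resected during protocol therapy for reasons other than progression".
- Section 10.2 asks for lesion-level data: "Any lesions that were surgically resected since the last imaging assessment should be explicitly noted", with the date, the reason and whether the lesion was growing.
- Section 13.1.8.2 makes "Any surgical tumor resection performed for lesions that are increasing in size" a cause of removal from therapy. Section 10.2.5.1 then assigns progression at the time of resection to "Patients who are removed from protocol therapy for resection of lesions that are increasing in size".
- Section 13.1.8.1 bars tumour resection in the first 12 weeks so that response can be assessed.

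No counterpart is written for radiotherapy. Section 10.2.3.1 has one note on lesions lying in an area irradiated earlier, and it concerns only whether they are measurable. Section 9.3 summarises radiotherapy practice descriptively under aim 1.3.1. Section 17.0 says that no radiation therapy is planned. Section 9.4 gives no event, censoring or sensitivity rule for on-study radiotherapy.

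**The concern.** Response and progression rest on the sum of target-lesion diameters, and the plan names one kind of locally treated lesion to leave out. An irradiated target lesion is not of that kind, so a site applying the text will keep it in. Local shrinkage is then credited to the study drugs.

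Two endpoints are exposed. A response produced by radiotherapy enters ORR, which section 9.3 treats as secondary. A delayed progression call enters PFS, the primary endpoint, where the final test uses 22 events and the futility look at 11 events turns on whether the observed hazard ratio exceeds 1.00. One event is 1/22 = 4.5% of the final information and 1/11 = 9.1% of the interim information.

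The documents describe no blinding, and progression has different consequences by arm: Arm C may cross over, while Arm A leaves protocol therapy. Use of radiotherapy could therefore differ between arms, although nothing in the documents shows that it will.

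**Working it through.** **The plan's own design figure.** Section 9.2 states at least 80% power for 22 events, hazard ratio 0.40 and one-sided alpha 0.15. Take a drift of (1 - HR)/(1 + HR) × √events. At HR 0.40 this is 0.4286 × √22 = 2.010. Against a critical value of 1.036, power without the interim look is Φ(2.010 - 1.036) = Φ(0.974) = 83.5%. Adding the stop at 11 events when the observed hazard ratio exceeds 1.00 (two-look normal approximation, simulated) gives 81.0%, 67.2% and 13.9% at HR 0.40, 0.50 and 1.0. The plan's table has 80%, 66% and 14%. The design figure is reproduced, and this point leaves it unchanged.

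**Inputs for the lesion arithmetic.** Section 10.2.5.1 gives the thresholds. Partial response: "At least a 30% decrease in the sum of the diameters of target lesions", measured from baseline. Progression: "At least a 20% increase in the sum of the diameters of target lesions", measured from the smallest sum on study, with an absolute increase of at least 5 mm. The lesion sizes and shrinkage below are assumptions: one irradiated lesion of 40 mm, other targets totalling 60 mm, baseline sum 100 mm, radiotherapy shrinkage 75%.

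**Step 1, response.** The irradiated lesion goes from 40 to 10 mm and the others stay at 60 mm.
- Lesion kept in: (60 + 10)/100 - 1 = -30%, partial response.
- Lesion excluded: 60/60 - 1 = 0%, stable disease.

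In general, let s be the irradiated share of the baseline sum and f its fractional shrinkage. Local treatment alone gives a partial response when s × f ≥ 0.30, for example s = 0.4 with f = 0.75, or s = 0.6 with f = 0.5.

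**Step 2, progression when no scan falls between shrinkage and growth.** The others go from 60 to 78 mm.
- Lesion excluded: 78/60 - 1 = +30% and +18 mm, which is progression after week 12.
- Lesion kept in: (78 + 10)/100 - 1 = -12%, stable disease.

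**Step 3, the same lesions when a scan records the nadir.** The recorded sum is 70 mm. Then 88/70 - 1 = +25.7% and +18 mm, which is progression. The masking in Step 2 therefore needs both changes to fall between the same two scans.

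**Step 4, growth the other targets need before progression is called** (20% if the irradiated lesion is excluded):
- Nadir not recorded: (0.20 + s·f)/(1 - s)
- Nadir recorded: 0.20 × (1 - s·f)/(1 - s)

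| s | f | Nadir not recorded | Nadir recorded |
|---|---|---|---|
| 0.3 | 0.5 | 50% | 24% |
| 0.4 | 0.5 | 67% | 27% |
| 0.5 | 0.5 | 90% | 30% |
| 0.4 | 0.75 | 83% | 23% |

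**Step 5, can both changes fall in one interval?** Imaging follows Cycles 2, 4, 6, 9 and 12, then every 4 cycles of 4 weeks. The gaps are 2 × 4 = 8 weeks up to Cycle 6, 3 × 4 = 12 weeks up to Cycle 12, and 4 × 4 = 16 weeks afterwards. It is possible, more easily later in treatment, but it is not the usual case to assume.

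**Step 6, surgery and radiotherapy compared.** A 40 mm lesion grows to 48 mm and the sum rises by 8/100 = 8%. If it is resected, any radiological increase suffices: the patient leaves therapy and has a PFS event. If it is irradiated, no event is recorded.

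**The case against.** The strongest reply is that this is silence, not a wrong rule. That is correct. A reader might infer that the protocol instructs sites to keep irradiated lesions in the sum, but no sentence says so; it follows only because the exclusion is confined to resected lesions. The measurability note in 10.2.3.1 might be used by some sites to drop such a lesion and by others to keep it. That makes classification less consistent and does not close the gap. Section 17.0 may mean that radiotherapy will be rare, but 4.2.2 still permits it.

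A reader might also infer that radiotherapy generally hides progression. The documents do not support this. Progression is judged from the smallest sum on study, and 10.2.5.1 repeats the nadir reference after any decrease. Once the nadir is on a scan, the extra growth needed is small (Step 4). New lesions and unequivocal progression of non-target lesions still count, subject to the 12-week exceptions in 10.2.1. In the first 12 weeks, growth of 20% to below 40% may in any case be handled as possible pseudoprogression.

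A third inference is that one arm is favoured. No radiotherapy rate is given, and crossover requires protocol-defined progression, so not even the direction is clear.

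Finally, one might copy the resection rule and call irradiation of any growing lesion progression. That would score palliative treatment after any increase in size as an event and would carry into removal and crossover, which are clinical-management matters. The objection stands against that remedy.

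**Conclusion.** The gap is real and limited. As written, shrinkage of a target lesion from on-study radiotherapy counts toward response, and it can offset growth in the other targets. In the worked case the response classification moves from 0% to -30%. A +30% growth elsewhere reads as -12% only when no scan separates the two changes; otherwise it reads as +25.7% and is called.

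This rests on assumed lesion sizes, an assumed 75% shrinkage, and the reading that an unlisted lesion stays in the sum. Frequency and imbalance by arm are unknown, so no effect on the hazard ratio, power or type I error can be given. The case for change is that the plan already accepts the principle for surgery, the primary analysis has few events, and the correction is cheap. The design calculation is not in question.

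**What to change.** For endpoint classification only:

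1. In 9.4, 10.2 and 10.2.5.1, extend the exclusion to lesions irradiated during protocol therapy. Their shrinkage then neither counts toward response nor offsets growth elsewhere. The baseline and nadir sums should be recomputed on the same remaining lesions.
2. State that later regrowth of an irradiated lesion can still count as progression. One way is to follow it as a non-target lesion under 10.2.5.2.
3. Record date, site, reason and growth status for each irradiated lesion, as is done for resected ones.
4. Add a PFS sensitivity analysis that counts irradiation of a growing lesion as an event.

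Irradiation of a growing lesion should not become a trigger for removal or crossover through this change. Because the criteria in 8.1 refer to 10.2, the sponsor should state whether the revised calculation also governs them, and should reconcile the differing treatment of surgery and radiotherapy in 4.2.2, 8.1 and 13.1.8.2.

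Cost: short edits to three sections, a few data fields and one extra analysis. Some patients will have fewer target lesions, and a patient whose target lesions are all irradiated will be assessed on non-target and new lesions. The 28-patient and 22-event targets stay as they are. The rule should be fixed before outcomes by arm are examined.
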